The high-risk non-cardiac surgical population represents a major global healthcare challenge. Recent estimates suggest that 234 million major surgical procedures are performed worldwide each year [1]. Complications following major surgery are a leading cause of morbidity and mortality [2-7]. Sickness absence to undergo surgery is second only to cardiovascular disease in terms of associated long-term mortality [2]. In the overall population, the incidence of post-operative complications and death is low. However, studies from the UK suggest a readily identified high-risk sub-group accounts for over 80% of post-operative deaths but less than 15% of in-patient procedures [5, 6]. In the UK, 170,000 patients undergo high-risk non-cardiac surgery each year [5, 6]. Of these patients, 100,000 will develop significant complications resulting in over 25,000 deaths [5-7]. Advanced age, co-morbid disease, major and urgent surgery are the key factors associated with increased risk [5-7]. This pattern of poor outcomes following major surgery can be readily identified worldwide [2-10]. Patients who develop complications but survive will still suffer reductions in functional independence and a substantial decrease in medium and long-term survival [2-4]. A prospective 13 year observational study of the Whitehall II cohort of 6478 British civil servants aged 35-55 examined the link between diagnoses associated with medical absence from work and long term all-cause mortality [2]. Physician-certified sickness absence attributable to undergoing a surgical operation was associated with a two-fold increased risk of mortality. Apart from circulatory disease, surgery was associated with the highest risk of later death compared to psychiatric, infectious, and respiratory disease. Despite strong evidence of the impact of poor surgical outcomes, our understanding of standards of care for patients undergoing major surgery is limited. In particular, little is known about the availability of critical care resources for non-cardiac surgical patients and the impact of critical care admission on clinical outcomes. Importantly, survival amongst patients who develop postoperative complications varies widely between hospitals, confirming both the potential and the need to improve clinical outcomes in this population [11].

Recent developments in peri-operative critical care may significantly improve outcomes for high-risk non-cardiac patients. However, new therapeutic approaches are unlikely to be translated into patient benefit unless suitable critical care facilities are available where they can be administered. In the UK, recent studies have demonstrated that fewer than one third of high-risk non-cardiac surgical patients are admitted to critical care following surgery [5, 6]. In addition, those patients who did receive this level of care were discharged after a median stay of 24 hours and subsequently lingered for many days on standard surgical wards. Premature discharge from critical care was identified as an important risk factor for post-

operative death, suggesting a failure to correctly identify those patients who can be discharged appropriately from critical care [5, 6]. This situation contrasts starkly with peri-operative care for cardiac surgical patients for whom post-operative critical care admission is routine. Cardiac surgical patients also have a high incidence of co-existing disease and undergo major surgery but with an overall mortality rate as low as 2% [12-15]. These observations may relate to poor availability of critical care beds in the UK. However published data do not support this suggestion [16], whilst other data suggest poor surgical outcomes are an international healthcare problem [2-11].

Little is known about standards of care for patients undergoing major non-cardiac surgery across Europe or clinical outcomes following such procedures. It has been suggested by some that poor surgical outcomes may vary between nations but this belief may simply reflect better recognition of the issue. Evidence from sources across the developed world suggests the existence of a large population of patients who can be readily identified as being at high risk of post-operative complications and death [2-10]. There is increasing recognition of the massive potential impact of even small improvements in peri-operative care [17, 18]. However, significant policy change can only be driven by robust and powerful data. Mismatch between critical care resource provision and peri-operative risk may be widespread or confined to a small number of nations. Either way, a rigorous evaluation of standards of peri-operative critical care across Europe would provide important data which could trigger a step-change in the current approach to care of the patient undergoing major non-cardiac surgery.

Research questions

1. What is the in-hospital mortality rate for patients undergoing non-cardiac surgery in Europe?
2. What is the duration of hospital stay for patients undergoing non-cardiac surgery in Europe?
3. What is the current standard of peri-operative critical care provision for patients undergoing non-cardiac surgery in Europe?
4. What is the current standard of haemodynamic (cardiac output) monitoring for patients undergoing non-cardiac surgery in Europe?
5. Is there any evidence of differences in the standard of peri-operative care provision for patients undergoing non-cardiac surgery in different health-care systems within Europe?
6. Is there any evidence of differences in hospital stay and mortality for patients undergoing major non-cardiac surgery in different health-care systems within Europe?
7. What factors determine planned and unplanned admission to critical care after surgery?
8. Are the factors associated with critical care admission similar to those associated with post-operative death?

Methods

Seven day, international cohort study of adult (≥ 16 years) patients undergoing in-patient non-cardiac surgery.

Inclusion criteria

Consecutive patients admitted to participating centres undergoing elective and non-elective non-cardiac surgery commencing during the seven day study period (00⁰⁰ day 1 to 24⁰⁰ day 7) with a planned overnight stay.

Exclusion criteria

Patients undergoing planned day-case surgery, cardio-thoracic surgery, neurosurgery, radiological or obstetric procedures.

Centres

We aim to recruit as many European centres as possible. We anticipate that a minimum of 150 hundred centres in ten or more nations will be required. We are hopeful that we can meet or exceed this target through the activities of national lead investigators and the support of key organisations such as the European Society of Intensive Care Medicine and the European Society of Anaesthesiology. Centres will receive an individual report allowing comparison of their dataset to that of their national cohort and of the overall dataset. We hope this will act as an incentive to participate.

Ethics approval

Ethics approval may not be required in all participating nations. National lead investigators will be responsible for clarifying the need for ethics approval and applying for this where appropriate. Centres will not be permitted to record data unless ethics approval or an equivalent waiver is in place. This study is in effect a large scale clinical audit. We expect that in most, if not every participating country, there will be no requirement for individual patient consent as all data will be anonymised and is already recorded as part of routine clinical care.

Data collection and collation

Data will be collected in individual centres on paper case record forms (CRFs). Data will then be pseudo-anonymised (coded) and transcribed by local investigators onto an internet based electronic CRF. The paper and electronic CRFs will be translated by the national lead investigators into the relevant languages (English, German, French, Italian, etc) and checked for consistency after back translation into English. CRFs will then be validated in each participating nation by the national lead investigators prior to patient recruitment. Paper CRFs will be stored within a locked office in each centre. This will include identifiable patient data in order to allow follow-up of clinical outcomes. Each centre will be identified by a numeric code and each patient will be assigned a numeric code at the point of electronic data entry. This will allow local investigators to identify individual patients whilst the co-ordinating study team cannot trace data back to an individual patient. Access to the data entry system will be protected by username and password. Username and password will be delivered during the registration process for individual local investigators. All electronic data transfer between participating centres and the co-ordinating centre will be username and password protected. Each centre will maintain a trial file including a protocol, local investigator delegation log, ethics approval documentation etc. A participant (patient) list will be used in each participating centre to match identifier codes in the database to individual patients in order to record clinical outcomes and supply any missing data points. Where individual centres are unable to access the internet based case record form, pseudo-anonymised (coded) facsimile (fax) data transfer will be available to a dedicated fax machine in the co-ordinating office. Pseudo-anonymised (coded) data may also be sent by mail to the coordinating centre if necessary.

Dataset

A realistic data set will be fundamental to the success of the investigation. We have identified the key data points whilst not discouraging centres from participating through an excessive burden of data collection. The reliability of data collection will be analysed formally using K-statistics or intra-class correlation coefficients as appropriate. National co-ordinators may request the addition of a limited number of data points to support the international EuSOS data collection and for subsequent national analyses. All additional data points must be discussed with the chief investigator and if necessary, the steering committee.

Form A: Centre specific data (collect once for each centre)

- Secondary/tertiary centre
- Number of operating rooms
- Number and level of critical care beds.
- Details about the reimbursement status of the hospital
- Public holidays or other local factors affecting patient throughput during study period

Form B: Individual patient data on all patients

Patient factors:

- Age
- Gender
- American Society of Anesthesiologists (ASA) grade
- Date of hospital admission
- Major co-morbid disease including:
 - Heart failure
 - Active cancer
 - Diabetes
 - Asthma / COPD
 - Renal failure

Surgical factors:

- Surgical procedure category
- Grade of surgery (minor, intermediate, major)
- Urgency of surgery (elective or non-elective)
- Duration of surgery (mins)
- Grade of surgeon
- Surgical checklist (Y/N)

Anaesthetic factors:

- Anaesthetic technique (general, regional, sedation)
- Haemodynamic (cardiac output) monitoring
- Airway (endotracheal, laryngeal mask, tracheostomy, etc)
- Grade of anaesthetist

Post-operative care:

- Duration of extended recovery stay (hours)
- Post-operative invasive ventilation within first 24 hours (planned / unplanned)
- Post-operative non-invasive ventilation within first 24 hours (planned / unplanned)
- Post-operative inotrope / vasopressor use within first 24 hours

Follow-up data:

- Date of Hospital discharge
- In-hospital mortality

Form C: Individual patient data for those admitted to critical care**Critical Care admission:**

- Body height and mass
- Critical care admission: Date and time
- Critical care admission: planned/unplanned
- Critical care admission: time since surgery
- Detailed co-morbidities
- Airway at ICU admission (endotracheal, laryngeal mask, tracheostomy, etc)
- Ventilatory support at ICU admission (invasive / non-invasive / none)
- Respiratory arrest prior to critical care admission
- Cardiac arrest prior to critical care admission
- Component data for SAPS III score
- SOFA score (one of four scores in each of six domains)

Physiological data following 24 hours in critical care:

- SOFA score (one of four scores in each of six domains)
- Respiratory support (invasive or non-invasive)
- Renal replacement therapy (planned or unplanned)

Physiological data following 48 and 72 hours in critical care:

- SOFA score (one of four scores in each of six domains)
- Respiratory support (invasive or non-invasive)
- Renal replacement therapy (planned or unplanned)

Follow-up data for patients admitted to critical care:

- Critical care discharge: Date and time
- SOFA score in last 24 hours of ICU stay (for patients staying ≥ 96 hours)
- Major therapeutic limitation during ICU stay (Y / N, date)
- Critical care discharge: planned or unplanned
- Critical care mortality

Sample size calculation

We anticipate that approximately 20,000 patients will be required to provide a sample of up to 2,000 admissions to critical care after surgery. Assuming an overall mortality rate following surgery of 1%, a sample size of 20,000 patients will yield 200 deaths. This will allow the inclusion of at least fifteen variables in a logistic regression model for mortality. The rate of admission to critical care is likely to vary between nations but an overall rate of 10% (either planned or unplanned) will yield data on 2000 admissions to critical care, whilst an overall rate of 5% will yield 1000 admissions. We expect this to allow a robust logistic regression model for this outcome. 20,000 patients will also provide >99% confidence for the overall mortality rate with 0.37% confidence width. This dataset would also have sufficient generalisability to inform the practice of peri-operative care on an international basis. If 200 deaths are observed in an overall sample of 20,000 patients, the 99% confidence interval for the proportion would be (0.0083 - 0.0120) with a confidence width of 0.37%. This dataset would also have sufficient generalisability to inform the practice of peri-operative care on an international basis.

Statistical analysis

The data to be collected are all collected as part of routine clinical care. Categorical variables will be described as proportions and will be compared using chi-square or Fisher's exact test. Continuous variable will be described as mean and standard deviation if normally distributed or median and inter-quartile range if not normally distributed. Comparisons of continuous variables will be performed using one-way ANOVA or Mann-Whitney test as appropriate. Uni-variate analysis will be performed to test factors associated with planned and unplanned admission to critical care and / or in-hospital death. A multiple logistic regression model will be used to identify independent risk factors. A stepwise approach will be used to enter new terms into the logistic regression model where $p < 0.05$ was set as the

limit for inclusion of new terms. A logistic regression model will be performed to assess independent association between prognostic factors and outcomes. Results of logistic regression will be reported as adjusted odds ratios (OR) with 95% confidence intervals. A single final analysis is planned at the end of the study.

Primary outcome measure

- In-hospital mortality

Secondary outcome measures

- Duration of hospital stay
- Planned admission to critical care
- Unplanned admission to critical care
- Duration of critical care stay

Organisation

Subject to funding approval, it is proposed that the EuSOS study will be conducted by the EuSOS study group on behalf of the European Society of Intensive Care Medicine and the European Society of Anaesthesiology. The steering committee will be chaired by RP. The study management team will be appointed by the steering committee and led by RP. The duties of this team will include administration of all project tasks, communication between project partners (including funders, steering committee members, national and local co-ordinators, etc), data collation and management and preparation of reports for individual study sites. The Steering committee is responsible for the scientific conduct and consistency of the project. The Steering committee will ensure communication between the funder(s), study management team and co-ordinators as necessary.

National co-ordinators

National co-ordinators will be appointed by the steering committee to lead the project within individual nations and:

- Identify local co-ordinators in participating hospitals
- Assist with translation of study paperwork as required
- Ensure distribution of research manuals, eCRF and other materials
- Ensure necessary regulatory approvals are in place prior to the start date
- Ensure good communication with the participating sites in his/her nation

Local co-ordinators

Local co-ordinators in individual institutions will have the following responsibilities:

- Provide leadership for the study in their institution
- Ensure all relevant regulatory approvals are in place for their institution
- Ensure adequate training of all relevant staff prior to data collection
- Supervise daily data collection and assist with problem solving
- Act as guarantor for the integrity and quality of data collected
- Ensure timely completion of eCRFs
- Communicate with the relevant national coordinator

Data management and ownership

On behalf of the steering committee, Queen Mary's University of London will act as custodian of the data. The Steering committee will retain the right to use all pooled data for scientific and other purposes. Members of the EuSOS study group will have the right to access the pooled data for research purposes provided the research proposal has been reviewed and deemed satisfactory by the Steering committee. The primary consideration for such decisions will be the quality and validity of any proposed analysis. Only summary data will be presented publicly and all institutions will be anonymised except in the individualised report provided to each institution at the end of the study. Individual patient data provided by participating sites remain the property of the respective institution.

Publication plan

Data will be presented and disseminated in a timely manner. In discussion with the funder(s), the steering committee will appoint a writing committee to draft the scientific report(s) of this investigation. Specific funding is requested to allow publication of data on an open access basis. On request, centres will be provided with an individual report allowing comparison of their individual centre's summary data to that of their national cohort and the overall dataset. In line with the principles of data preservation and sharing, the steering committee will, after publication of the overall dataset, consider all reasonable requests to make the dataset available in whole or part for secondary analyses and scientific publication. The steering committee will consider the scientific validity and the possible effect on the anonymity of participating centres prior to granting any such requests. Where appropriate, a prior written agreement will set out the terms of such collaborations. The steering committee will consider proposals for secondary analyses on the basis of the scientific quality of the proposal. National groups may wish to perform secondary analyses specifically of their

national dataset. Such proposals are generally encouraged and the Steering committee will make the national datasets available to national co-ordinators on receipt of a national study proposal. However, the steering committee must approve the final version of all manuscripts prior to submission, whether they relate to part or all of the EuSOS dataset.

Deliverables

The main deliverables will be scientific reports of preliminary findings for general and specialty journals, abstracts for presentation to national and international meetings including those of the supporting societies and a final report summarising the overall findings.

References

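### Research question 8 compares the factors for critical care admission with those for death, but stepwise selection at p<0.05 on outcomes with about 1,000-2,000 versus 200 events is likely to give different factor sets through unequal power alone

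*Protocol*

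**What the plan says.** Protocol, Research questions, item 8, asks: "Are the factors associated with critical care admission similar to those associated with post-operative death".

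Protocol, Sample size calculation, gives the expected events. For death: "Assuming an overall mortality rate following surgery of 1%, a sample size of 20,000 patients will yield 200 deaths". For critical care: "an overall rate of 10% (either planned or unplanned) will yield data on 2000 admissions to critical care", and "an overall rate of 5% will yield 1000 admissions". On model size for death it adds: "This will allow the inclusion of at least fifteen variables in a logistic regression model for mortality".

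Protocol, Statistical analysis, plans univariate screening of factors for planned admission, unplanned admission and in-hospital death. Multiple logistic regression is then used to find independent risk factors: "A stepwise approach will be used to enter new terms into the logistic regression model where" p<0.05 is the entry limit. A further sentence plans a logistic model for the independent association of prognostic factors with outcomes. Odds ratios after adjustment are to be reported with 95% intervals.

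The section names no covariate set common to the two outcomes, no contrast of coefficients between them and no criterion for similarity. Planned and unplanned admission are separate secondary outcomes. Question 8 does not say whether they are pooled.

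**The concern.** Question 8 is about whether two sets of associations agree. Under the stated rule, a factor enters a model by passing p<0.05, and whether it passes depends on the number of events as well as on the size of the effect. By the protocol's own figures, admissions outnumber deaths five- to ten-fold. A factor with the same true odds ratio for both outcomes can easily be kept in the admission model and dropped from the death model.

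Two things follow:

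- The lists of selected factors can disagree when the underlying effects do not.
- Reporting odds ratios does not fully repair this. A factor left out of the death model has no adjusted odds ratio to compare, and factors kept in both models are adjusted for different companions.

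The protocol's background presents a possible mismatch between critical care provision and peri-operative risk as a reason for the study, so an artefact in the answer to question 8 could be over-read.

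**Working it through.** **Events, from the protocol.**
- Deaths: 20,000 × 0.01 = 200.
- Admissions: 20,000 × 0.10 = 2,000, or 20,000 × 0.05 = 1,000.
- Death model with fifteen variables: 200/15 = 13.3 events per variable.

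These reproduce the protocol's counts.

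**Assumptions, not from the protocol.** One binary factor with prevalence q = 0.20, independent of the others, with the same odds ratio (OR) for both outcomes. The p<0.05 limit is taken as two-sided, since the protocol does not say.

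**Chance that one factor passes p<0.05.** SE(log OR) = 1/√[N·p·(1−p)·q·(1−q)] with N = 20,000 and p the event rate. Power = Φ(ln OR/SE − 1.96), where the opposite tail is negligible. ln 1.3 = 0.262, ln 1.5 = 0.405, ln 2 = 0.693.

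| Events | p | SE | OR 1.3 | OR 1.5 | OR 2.0 |
|---|---|---|---|---|---|
| 200 (death) | 0.01 | 0.178 | 32% | 63% | 97% |
| 1,000 (admission) | 0.05 | 0.081 | 90% | >99% | >99% |
| 2,000 (admission) | 0.10 | 0.059 | >99% | >99% | >99% |

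Worked line: 1/√(20,000 × 0.01 × 0.99 × 0.16) = 0.178; 0.262/0.178 = 1.48; Φ(1.48 − 1.96) = 0.315.

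A version that takes the variance separately in patients with and without the factor gives 35%, 93% and >99% at OR 1.3, so the picture does not depend on the approximation.

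**If planned and unplanned admissions are modelled separately.** The split is not given. If one type makes up 25-50% of admissions, its model has 250 to 1,000 events. At OR 1.3 the same formula gives 38% with 250 events, 64% with 500, 81% with 750 and 90% with 1,000, against 32% for death. The gap narrows, and nearly closes only at about 250 events.

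**Direction of the artefact.** At OR 1.3, treating the two selections as independent:
- Kept for admission, dropped for death: (1 − 0.315) × 0.899 = 62% with 1,000 admissions; (1 − 0.315) × 0.994 = 68% with 2,000.
- Kept for death, dropped for admission: 0.315 × (1 − 0.899) = 3%; 0.315 × (1 − 0.994) = 0.2%.

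**Stepwise selection itself.** Single-factor power is only a proxy for stepwise retention, so forward selection was simulated: score test, entry at p<0.05, 20,000 patients, 15 independent binary candidates with prevalence 5-50%, identical true ORs for both outcomes, 60 replicates.

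| True ORs | Mean true factors selected with 200 / 1,000 / 2,000 events | Lists differ, 200 vs 1,000 or 2,000 | Mean number of factors differing | Control: 2,000 vs 2,000 events |
|---|---|---|---|---|
| 12 factors at 1.2-2.0, 3 null | 6.4 / 10.7 / 11.6 | 100% | 5.3-5.7 | 67%, by 1.0 |
| 12 factors at 1.2-3.0, 3 null | 9.1 / 11.4 / 11.9 | 97-100% | 3.1-3.2 | 47%, by 0.5 |
| 15 factors at 2.0-2.5 | 14.5 / 15 / 15 | 43% | 0.5 | 0% |

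The control column shows that stepwise selection causes some disagreement even with equal events. Most of the disagreement comes from the unequal event counts.

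**The case against.** Several points on the other side are fair.

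- **A reader might infer that question 8 will be decided by comparing the two lists.** The protocol does not say so. It also plans univariate analyses and reports odds ratios with intervals, which a careful reader could set side by side, and an SAP that is not shown may give the method. This stands, and stepwise selection is not the only analysis offered. It does not remove the problem: the rule that is stated produces adjusted odds ratios for different factors and with different adjustment, so the side-by-side comparison is incomplete.
- **A reader might infer that the lists are bound to differ.** They are not. When every odds ratio is about 2 or more, they differed in fewer than half of the simulated replicates, by half a factor on average. The near-certain disagreement needs some effects in the range of about 1.2 to 1.5, and the protocol gives no effect sizes either way.
- **A reader might infer that the plan leans towards showing that critical care misses those at risk of death.** That conclusion needs predictors of death that are absent from the admission model, which is the rare pattern (about 3% or less per factor above). The usual artefact is an admission factor that death does not confirm. The protocol itself says only that mismatch may be widespread or may be limited to a few nations.
- **The five- to ten-fold contrast pools planned and unplanned admissions.** Correct. Separate models would have a smaller contrast.

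**Conclusion.** The point holds in a limited form. Stepwise entry at p<0.05 suits question 8 badly, because it ties what counts as a risk factor to the number of events, and the two outcomes differ five- to ten-fold on the protocol's figures when admissions are pooled. For a shared factor with 20% prevalence and odds ratio 1.3, retention is about 32% for death and 90% to over 99% for admission. At odds ratio 1.5 it is 63% against over 99%, and at 2.0 the gap has largely gone (97% against over 99%).

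Differences between the selected sets are therefore weak evidence that the factors differ. The event counts are the protocol's. The prevalences, odds ratios and independence between factors are assumptions. This goes beyond detail that an SAP might supply, because the selection rule the protocol does state is a poor fit for the question it asks.

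**What to change.** For question 8, pre-specify one covariate set from Form B, which is collected on all patients. About fifteen variables fits the protocol's own allowance for the death model. Fit that set to both outcomes in the same patients without stepwise selection, stating whether admissions are pooled or split by type. Report both sets of odds ratios with 95% intervals, and base the answer on them, not on which terms reach p<0.05. A ratio of odds ratios per factor, with an interval from a stacked model or a bootstrap that allows for clustering by hospital, is one direct way to do this.

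**Cost.** One paragraph and a little more analysis; no new data. The ratios will be imprecise because there are only about 200 deaths. At 20% prevalence, ignoring correlation between the two estimates and clustering, the SE of the log ratio is √(0.178² + 0.081²) = 0.195 with 1,000 admissions, and exp(1.96 × 0.195) = 1.47. Each ratio would be known to within a factor of roughly 1.5 either way. With 2,000 admissions the factor is 1.44, so more admissions help little. That imprecision is a limit of the data, and the report should show it.

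### The planned precision for in-hospital mortality (99% CI width 0.37%) assumes independent patients, although whole hospitals within nations are sampled and the named analyses are single-level

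*Protocol*

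**What the plan says.** The Protocol's sample size section begins: "We anticipate that approximately 20,000 patients will be required". It then gives the mortality assumption, "Assuming an overall mortality rate following surgery of 1%, a sample size of 20,000 patients will yield 200 deaths", and says of the resulting precision that "the 99% confidence interval for the proportion would be (0.0083 - 0.0120) with a confidence width of 0.37" per cent. The same section also describes this as more than 99% confidence in the overall mortality rate.

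The sampling is by hospital. The inclusion criteria take "Consecutive patients admitted to participating centres undergoing elective and non-elective non-cardiac surgery commencing during the seven day study period", and the section on centres states: "We anticipate that a minimum of 150 hundred centres in ten or more nations will be required". I read the number as 150. The background text reports that "survival amongst patients who develop postoperative complications varies widely between hospitals".

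The statistical analysis section names chi-square and Fisher tests, ANOVA and Mann-Whitney tests, and a stepwise regression: "A multiple logistic regression model will be used to identify independent risk factors". It names no hospital or nation term, random effect, generalised estimating equation or cluster-robust variance. The only intra-class correlation in the Protocol, in the Dataset section, concerns the reliability of data collection.

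**The concern.** Patients in the same hospital share case mix, staff, critical care provision and discharge practice, so their outcomes are correlated. With any positive ICC, 20,000 patients from about 150 hospitals carry less information on a mortality rate than 20,000 independent patients. A precision figure that ignores this promises more than the design can deliver.

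Two parts of the study are exposed. The first is the overall in-hospital mortality rate, which is research question 1 and the primary outcome. The second is any contrast between hospitals, nations or health-care systems, which covers research questions 5 and 6 and the hospital characteristics on Form A. For such factors the hospital, not the patient, is close to the effective unit. A patient-level test would declare differences too often, and a stepwise procedure with entry at p < 0.05 would carry those false positives into the final model.

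**Working it through.** **Inputs from the Protocol.** n = 20,000; 200 deaths, so p = 0.01; 99% confidence (sample size section). 150 hospitals (section on centres), so m = 20,000/150 = 133.3 patients per hospital.

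**Inputs assumed.** ICC for mortality from 0.001 to 0.02; equal hospital sizes in the main table; no additional nation-level clustering.

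**Step 1: reproduce the stated interval.** For 200/20,000 at 99%:

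| Method | Interval | Width |
|---|---|---|
| Exact binomial (Clopper-Pearson) | 0.00828 to 0.01196 | 0.368% |
| Wilson | 0.00834 to 0.01198 | 0.364% |
| Wald | 0.00819 to 0.01181 | 0.362% |

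Of these, the exact interval matches both printed limits and the printed width. The arithmetic is right. All three methods assume independent patients, that is, a design effect of 1.

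**Step 2: allow for clustering.**

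- Design effect: DE = 1 + (m − 1) × ICC = 1 + 132.3 × ICC
- Effective sample size: 20,000/DE
- 99% width: 2 × 2.576 × √(p(1 − p) × DE/n) = 0.362% × √DE
- True coverage of a nominal 99% interval: 2Φ(2.576/√DE) − 1
- Type I error of a nominal 5% test of a factor constant within hospital: 2(1 − Φ(1.96/√DE))

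Example, ICC 0.01: DE = 1 + 1.323 = 2.32; effective n = 20,000/2.323 = about 8,600; width = 0.362% × 1.524 = 0.55%.

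| Assumed ICC | DE | Effective n | 99% width | True coverage | Type I error |
|---|---|---|---|---|---|
| 0.001 | 1.13 | 17,700 | 0.39% | 98.5% | 6.5% |
| 0.0025 | 1.33 | 15,000 | 0.42% | 97.4% | 8.9% |
| 0.005 | 1.66 | 12,000 | 0.47% | 95.4% | 12.8% |
| 0.01 | 2.32 | 8,600 | 0.55% | 90.9% | 19.8% |
| 0.02 | 3.65 | 5,500 | 0.69% | 82.3% | 30.5% |

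Coverage is computed for the Wald interval. The exact interval is slightly wider (0.368% against 0.362%), so its coverage would be higher by less than a percentage point.

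**Step 3: put the ICC on a readable scale.** On the proportion scale, ICC = SD²/(p(1 − p)), where SD is the between-hospital standard deviation of mortality. An SD of 0.5 percentage points around 1% gives 0.005²/0.0099 = 0.0025. An SD of 1 point gives 0.01²/0.0099 = 0.010. The table thus runs from √(0.001 × 0.0099) = 0.31 points to √(0.02 × 0.0099) = 1.4 points.

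**Step 4: unequal hospital sizes.** With coefficient of variation CV of hospital size, DE = 1 + ((1 + CV²)m − 1) × ICC. For an assumed CV of 0.8 the widths at the five ICCs become 0.40%, 0.45%, 0.52%, 0.65% and 0.84%. Clustering by nation would add to this.

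**The case against.** The strongest defence is that the effect may be small. At ICC 0.001 the width is 0.39% against 0.37%, which would trouble nobody. The Protocol's remark on variation between hospitals concerns patients with complications, not a cohort that includes minor surgery, so it makes a positive ICC plausible without indicating its size. This stands: a reader might infer from the upper rows of the table that the precision is badly overstated, but the documents do not establish that.

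A reader might also infer that every interval from the logistic models is too narrow. That does not follow. Most Form B predictors (age, ASA grade, comorbidity, urgency) vary within hospitals, and ignoring clustering need not narrow their intervals.

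It can be said too that the interval is a planning illustration, that the number of critical care admissions and the deaths per model variable also support the sample size, and that the statistical analysis plan, which is not shown, may specify a hierarchical model. These points are fair and limit the criticism of the analysis section. They do not rescue the precision statement, which the Protocol itself makes and which a later plan would not correct.

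A further tempting reading is that the Protocol contradicts its own 1% mortality. The background says that "a readily identified high-risk sub-group accounts for over 80% of post-operative deaths but less than 15% of in-patient procedures", with 25,000 deaths among 170,000 high-risk patients in the UK. Taking both shares at their limits gives (25,000/170,000) × (0.15/0.80) = 2.76%. But that is a ceiling from one country. Overall mortality of 1% needs a high-risk share of between 0.01 × 0.80/0.147 = 5.4% and 0.01/0.147 = 6.8% of procedures, which satisfies the stated limit of under 15%. There is no contradiction. The printed number of centres is a clerical slip with no consequence beyond the reading made here.

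**Conclusion.** The concern holds for the stated precision, and for the overall mortality rate and hospital-, nation- or system-level comparisons if they are analysed with the single-level methods named. The direction is certain for any positive ICC: the true width exceeds 0.37%, and tests of factors constant within hospitals reject too often. The size is not certain. At ICC 0.0025, a between-hospital SD of half a percentage point, the width is 0.42% and the type I error 8.9%. At ICC 0.01 they are 0.55% and 19.8%.

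These figures rest on 150 equally sized hospitals, 1% mortality, assumed ICCs and no separate nation-level effect. Unequal sizes and clustering by nation would widen them. They describe mortality; the ICCs for critical care admission and length of stay are not given either and may differ.

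**What to change.** In the sample size section, replace the 0.37% width and the claim of more than 99% confidence with the 99% CI width over a stated ICC range, giving the assumed number of hospitals and the allowance for unequal sizes.

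In the statistical analysis section, state that the CI for overall mortality, and all comparisons and regressions, will account for clustering by hospital and nation. A multilevel logistic model would do this, as would nation terms with hospital-cluster-robust variance. The second has some appeal, since there may be only ten nations and about 200/150 = 1.3 expected deaths per hospital, and random nation effects shrink the contrasts that research questions 5 and 6 ask about. The choice can be left to the statistical analysis plan, provided the principle is fixed in the Protocol.

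The cost is a less favourable precision statement and a slightly more complex analysis. Hospital codes are already recorded and nation follows from them, so no extra patients or data are needed.
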